4.1 Metastatic Non-Small Cell Carcinoma

Non-small cell carcinoma (NSCLC) is the ninth most common cancer in Australia and the fourteenth most common cancer worldwide (1, 2). The incidence of NSCLC is rising, particularly in patients aged 70 to 90 years (3). Overall, 17% of patients present with metastatic disease and another 50% of patients initially treated with curative intent will develop metastatic disease (4, 5). Historically patients with metastatic non-small cell carcinoma (mNSCLC) have a poor prognosis, with 5-year survival rates of ≤10% (6). In patients with metastatic disease, the median survival time ranges from 6 to 12 months, and in patients with brain metastases, the mean survival time is 3 months (7, 8).

4.2 Stereotactic Ablative Body Radiotherapy and Evidence in Oligometastatic Malignancies.

There is a large body of literature on SABR for oligometastatic malignancies. For practical reasons only the landmark SABR oligometastatic studies will be summarized to highlight tolerability and efficacy.

Salama and colleagues (1) reported on patients with 1 to 5 metastatic cancer sites based on 18F-fluorodeoxyglucose positron emission tomography (FDG-PET) imaging and a life expectancy of at least 3 months who were treated with SABR. Patients received escalating doses of RT, starting at a dose 24Gy (three 8Gy fractions) 2Gy per fraction dose-escalations and a dose ceiling of 60Gy (three 20Gy fractions). The commonest metastatic sites treated were lung (36.3%), lymph nodes (19.4%), liver (19.4%), bone (13.3%) and adrenal glands (8.0%). At a median follow up of 20.9 months no dose limiting toxicity was seen. One patient with a centrally located right upper lobe metastases who received 36Gy (three 12Gy) fractions developed haemoptysis 10 months after SABR. CT and bronchoscopy revealed disease recurrence and this patient died shortly afterwards. More recent studies due to toxicity recommend excluding central lung lesions outside the contexts of clinical trials (2).

A number of phase I and II studies of SABR to spinal metastasis have demonstrated favourable local disease control rates (86-90%) for patients without spinal cord compression (3-6). Similar to intracranial stereotactic radiosurgery, SABR has been shown to be effective in the retreatment of metastases that progress following standard EBRT (7). Additionally, SABR has been shown to be very effective in palliating pain associated with spinal metastases (8, 9).

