4.5 Summary of Risks and Benefits

SABR involves highly hypofractionated radiotherapy given as an ablative treatment. While there is extensive literature suggesting that it is safe and has low rates of major toxicities, such studies have tended to have small numbers and relatively short follow up given most patients succumb to their metastatic disease. The risk of treatment depends on the exact anatomical site of the metastatic disease irradiated. There is a low but not negligible risk of radiation pneumonitis, bone fractures, radiation enteritis, skin fibrosis, renal impairment and proctitis. There is an exceedingly low risk of transverse myelitis.

SABR is thought to provide long-term local control of irradiated sites of cancer. It also provides good and durable pain relief for painful metastases. It is postulated that SABR to sites of oligometastatic or oligoprogressive non-small cell carcinoma, in selected patients, may prolong survival. Clearly studies that determine whether a survival benefit occurs with such treatment remain to be conducted and reported.

It is acknowledged that patients may have received previous radiotherapy to an area where SABR is to be delivered in this protocol (equivalent dose of 30 Gy in 10 fractions). Due to the increased dose that is received in this instance, there is an increased risk of radiation toxicity in these patients. This potential increased level of risk has been highlighted in the patient information and consent form and must be discussed in each instance prior to informed consent. Patients who have received more than this RT equivalent dose schedule to an area planned for further SABR treatment are not eligible for this study. Additionally, as there is a risk of pneumonitis with both pembrolizumab (discussed below) and radiotherapy, patients who have received more than 36Gy in 12 fractions (or equivalent) of radiotherapy to the lung within 6 months of study screening will be considered ineligible.

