Eligible patients will be randomised to either:

Arm 1: SABR followed by pembrolizumab; *or*

Arm 2: Pembrolizumab followed by SABR after cycle 1

Refer to Trial Schema

Pembrolizumab at a dose of 200 mg will be delivered every 3 weeks for a total duration of 102 weeks (34 cycles), commencing either 7 days (+/- 2 days) before the first dose of SABR or 7 days (+/-2 days) after the last dose of SABR.

Tumour response will be assessed according to RECIST 1.1, and irRECIST, Peter Mac Metabolic Response Criteria and PERCIST 1.0. Responses will be characterized in lesions treated with SABR and in un-irradiated lesions.

Peripheral blood samples and where possible, tumour tissue will be collected pre, during and post-treatment to assess baseline findings and longitudinal changes in immune subsets within tumour tissue and peripheral blood.

Evaluable patients are those that receive at least one dose of pembrolizumab and one dose of SABR. Non-evaluable patients will be replaced until the planned sample size has been reached.

7. Study Population

Patients with metastatic NSCLC who meet the inclusion/exclusion criteria described below will be eligible for participation in this study.

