7.2 Exclusion Criteria

The patient must be excluded from participating in the trial if the patient:

1. Has had previous high dose radiotherapy (biological equivalent of >30Gy in 10#) to an area to be treated which includes vertebral bodies (see below).

Note: Previous high dose radiotherapy is defined as a biological equivalent dose to above that of 30 Gy in 10 fractions using an alpha/beta ratio (50) of 3. Where a patient has received radiotherapy to an equivalent or lower dose than defined above, stereotactic radiotherapy of the area may be considered. In doing so, assessment of the volume and total dose received by any overlap region must be made, and documented by generating a cumulative plan incorporating both the previous and current treatment fields. It is the treating radiation oncologist's responsibility to review both the current plan and the cumulative plan inclusive of previous radiotherapy.

2. Has had previous thoracic radiotherapy of > 36Gy within the 6 months prior to randomisation.
3. Has known active central nervous system (CNS) metastases and/or carcinomatous meningitis. Patients with small asymptomatic or previously treated brain metastases may participate provided they are stable (without evidence of progression by imaging for at least four weeks prior to the first dose of trial treatment and any neurologic symptoms have returned to baseline), have no evidence of enlarging brain metastases, and are not using steroids for intracranial neurological symptoms at least 7 days prior to trial randomisation. This exception does not include leptomeningeal disease which is excluded regardless of clinical stability.
4. Has evidence of Spinal Cord Compression.
5. Has a Spinal Instability Neoplastic Score ≥ 7 unless lesion reviewed by a neurosurgical service and considered stable (see Appendix 2).
6. Requires surgical fixation of bone lesion for stability. All surgical fixation and instrumentation must be completed before randomisation on study.
7. Is currently participating and receiving study therapy or has participated in a study of an investigational agent and received study therapy or used an investigational device within 4 weeks of randomisation.
8. Has a diagnosis of immunodeficiency.
9. Has a known history of active TB (Bacillus Tuberculosis)
10. Has a hypersensitivity to pembrolizumab or any of its excipients.

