11. Has had a prior anti-cancer monoclonal antibody (mAb) within 4 weeks prior to randomisation or who has not recovered (i.e., \leq Grade 1 or at baseline) from adverse events due to agents administered more than 4 weeks earlier.
12. Has diagnosed and/or treated additional malignancy within 5 years prior to randomisation with the exception of: curatively treated basal cell carcinoma of the skin, squamous cell carcinoma of the skin, curatively treated early stage cervical

cancer, breast cancer or prostate cancer with no evidence of active disease. Other exceptions may be considered following consultation with the principal investigator

13. Has active autoimmune disease that has required systemic treatment in the past 2 years (i.e. with use of disease modifying agents, corticosteroids or immunosuppressive drugs). Replacement therapy (e.g. thyroxine, insulin, or physiologic corticosteroid replacement therapy for adrenal or pituitary insufficiency, etc.) is not considered a form of systemic treatment.
14. Has a history of (non-infectious) pneumonitis that required steroids or current pneumonitis.
15. Has had any systemic anti-cancer therapy or radiation therapy within 4 weeks prior to randomisation
16. Has known interstitial lung disease
17. Has an active infection requiring systemic therapy.
18. Has a history or current evidence of any condition, therapy, or laboratory abnormality that might confound the results of the trial, interfere with the patient's participation for the full duration of the trial, or is not in the best interest of the patient to participate, in the opinion of the treating investigator.
19. Has known psychiatric or substance abuse disorders that would interfere with cooperation with the requirements of the trial.
20. Has received prior therapy with an anti-PD-1, anti-PD-L1, or anti-PD-L2 agent.
21. Has a known history of Human Immunodeficiency Virus (HIV) (HIV 1/2 antibodies).
22. Has known active Hepatitis B (e.g., HBsAg reactive) or Hepatitis C (e.g., HCV RNA [qualitative] is detected).
23. Has received a live vaccine within 30 days of randomisation.

Note: Seasonal influenza vaccines for injection are generally inactivated flu vaccines and are allowed; however intranasal influenza vaccines (e.g., Flu-Mist®) are live attenuated vaccines, and are not allowed.

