7.3 Patient Registration/Randomisation

Recruitment will cover a 2-year period. Screening for individual patients will take place within 28 days prior to randomisation onto the study.

The Investigator should ensure that all requirements are met prior to randomisation of eligible patients on the trial:

- Patient meets all inclusion and exclusion criteria requirements
- Patient has signed and dated all applicable consent forms
- All screening assessments have been completed and recorded in the patient's medical records complete with all relevant source documents

Eligible patients will be randomised electronically using the online SABRseq electronic data capture (EDC) system. Confirmation of randomisation and randomisation ARM will be provided electronically (via email) as well as, a unique 5-digit patient identification number.

Patients will not be randomised if treatment has commenced or if consent has not been given. Once a patient is randomised on a trial, randomisation will not be cancelled.

Following randomisation, patients should begin protocol treatment within 28 days

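### Exclusion 2 in 7.2 drops the fraction-adjusted lung limit of 4.5, so some recent large-fraction lung courses outside the SABR area pass the eligibility list although 4.5 bars them

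*Combined protocol and SAP*

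**What the plan says.** Section 4.5 (Summary of Risks and Benefits) notes that radiotherapy and pembrolizumab can both cause pneumonitis. For that reason, patients who have had "more than 36Gy in 12 fractions (or equivalent) of radiotherapy to the lung within 6 months of study screening will be considered ineligible".

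Section 7.2, exclusion 2, is the matching entry in the eligibility list: "Has had previous thoracic radiotherapy of > 36Gy within the 6 months prior to randomisation". It gives no number of fractions and no equivalence. It also says thoracic where 4.5 says lung, and counts back from randomisation where 4.5 counts back from screening.

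Exclusion 1, directly above it, does adjust for fractionation. It defines prior high-dose radiotherapy as a "biological equivalent dose to above that of 30 Gy in 10 fractions using an alpha/beta ratio (50) of 3", but applies only to an area that is to be treated.

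Enrolment runs on the 7.2 list. Section 7 (Study Population) says that patients "who meet the inclusion/exclusion criteria described below will be eligible for participation in this study", and the pre-randomisation check in 7.3 is "Patient meets all inclusion and exclusion criteria requirements". Section 7.3 adds that a randomisation, once made, is not cancelled.

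**The concern.** Both texts are current and concern the same hazard, but they can give different answers for the same patient. A site that applies the 7.2 list correctly could randomise someone whom 4.5 calls ineligible. The protocol treats fraction size as relevant in 4.5 and in exclusion 1, and gives no reason for leaving it out of exclusion 2.

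What is at stake is patient safety and clear eligibility. Toxicity is the primary endpoint (5.3), with 16 patients per arm. Under 14.10, three or more treatment-related grade 3-4 cases of pneumonitis or colitis prompt a review that may close the trial. The point applies equally to both arms.

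**Working it through.** The plan gives no figure to reproduce here, so the check compares the two rules on a common scale.

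**Inputs.** The 4.5 limit is 36 Gy in 12 fractions or equivalent. The exclusion 2 limit is a total above 36 Gy. Exclusion 1 uses alpha/beta 3. Section 4.5 states no alpha/beta, so 2 to 10 is assumed and the results are shown at 2, 3 and 10.

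**Formula.** For total dose D in n fractions, BED = D × (1 + (D/n)/(alpha/beta)). At alpha/beta 3:

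- 36 Gy in 12: 36 × (1 + 3/3) = 72
- 18 Gy in 1: 18 × (1 + 18/3) = 126
- 30 Gy in 5: 30 × (1 + 6/3) = 90
- 36 Gy in 3: 36 × (1 + 12/3) = 180

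| Course | BED at 2 | at 3 | at 10 | Over 36 Gy (7.2)? | Over 4.5 limit? |
|---|---|---|---|---|---|
| 36 Gy in 12 (the limit) | 90 | 72 | 46.8 | – | – |
| 18 Gy in 1 | 180 | 126 | 50.4 | No | Yes, at all three |
| 20 Gy in 1 | 220 | 153.3 | 60 | No | Yes, at all three |
| 30 Gy in 5 | 120 | 90 | 48 | No | Yes, at all three |
| 36 Gy in 3 | 252 | 180 | 79.2 | No | Yes, at all three |
| 24 Gy in 3 | 120 | 88 | 43.2 | No | Only below alpha/beta 7 |
| 20 Gy in 5 | 60 | 46.7 | 28 | No | No |
| 25 Gy in 5 | 87.5 | 66.7 | 37.5 | No | No |
| 30 Gy in 10 | 75 | 60 | 39 | No | No |

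**Crossover.** Setting D + D²/(n × r) = 36 + 108/r and solving for r = alpha/beta gives r = (D²/n − 108)/(36 − D).

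- 18 Gy in 1: (324 − 108)/18 = 12.
- 30 Gy in 5: (180 − 108)/6 = 12.
- 36 Gy in 3 exceeds the limit at every ratio, because its total is the same and its fractions are larger.

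The three lead examples therefore do not depend on the choice of ratio within 2 to 10.

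**Reverse case.** At alpha/beta 3, 40 Gy in 20 has BED 66.7 and 45 Gy in 25 has exactly 72. Both fail exclusion 2 but do not exceed the 4.5 limit. This direction depends on the ratio: at alpha/beta 10, 40 Gy in 20 is 48, above 46.8.

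**What else in 7.2 might catch these courses.**

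- Exclusion 1 has a limit of 30 × (1 + 3/3) = 60 at alpha/beta 3. All three lead examples exceed it, so they are caught if that area is to be treated again, but not otherwise.
- Exclusion 15, "Has had any systemic anti-cancer therapy or radiation therapy within 4 weeks prior to randomisation", covers only the most recent 4 weeks.
- Exclusions 14 and 16 concern pneumonitis that is current or needed steroids, and interstitial lung disease. They set no dose.
- Exclusion 18 is the investigator's judgement and sets no dose.

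What is left is a lung course outside the planned SABR area, given between 4 weeks and 6 months before randomisation.

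**Start date.** Screening falls within the 28 days before randomisation (7.3), so 4.5 looks back up to 28 days further than 7.2.

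**The case against.** The strongest reply is that both rules are exclusions and can be obeyed together. Section 15.3 requires the whole protocol to be read and followed, so a patient barred by either text should not be enrolled. That is right as a reading of the document. It does not remove the gap, because the check named in 7.3 is against the criteria list and 4.5 is background text.

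A second reply is that the trial itself gives single fractions of 20 Gy, or 18 Gy to a central lung lesion (9.3), within about a week of pembrolizumab, so a prior 18 Gy to one lung site is an exposure of a kind the protocol accepts. This stands as a caution about risk. A reader might infer from 126 or 180 against 72 that these patients face about twice the pneumonitis hazard. The documents do not support that: BED at the prescription point ignores irradiated volume, and nothing in the protocol sizes the added risk. The figures compare two rules only.

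Third, how often this arises is unknown. Section 4.2 mentions "One patient with a centrally located right upper lobe metastases who received 36Gy (three 12Gy) fractions", and 9.1 says single-fraction SABR is the schedule used most at the sponsor's centre. The first is one patient in an outside study, and neither shows how many candidates for this trial had such a course in the relevant window.

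Fourth, reading the undefined equivalence in 4.5 as BED is an assumption. It is the same approach as exclusion 1, and the lead examples hold across the range tried.

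**Conclusion.** The point holds as an inconsistency in a safety eligibility rule. Lung courses such as 18 Gy in 1, 30 Gy in 5 or 36 Gy in 3, given between 4 weeks and 6 months before randomisation and outside the area planned for SABR, pass every dose-based criterion in 7.2 while 4.5 makes the patient ineligible. This rests on the linear-quadratic BED and an alpha/beta between 2 and 10.

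Three broader readings are not supported:

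- A reader might infer that any recent hypofractionated lung course slips through. Milder courses (20 Gy in 5, 25 Gy in 5, 30 Gy in 10) are eligible under both texts, and exclusions 1 and 15 catch others.
- A reader might infer that 7.2 is simply the looser rule. It is stricter for some conventional courses and covers a wider region.
- A reader might infer that the safety results or the design are compromised. No error rate, sample size or analysis changes. The pneumonitis dosing rules (10.1), the review trigger (14.10) and committee oversight (17.3) limit harm, though only after enrolment.

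The documents do not say which limit was intended. Only 4.5 gives a reason for its own.

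**What to change.** Amend exclusion 2 to bar either of two exposures in the 6 months before screening: thoracic radiotherapy totalling more than 36 Gy, or lung radiotherapy whose biological equivalent is above that of 36 Gy in 12 fractions. The clinical leads should state the alpha/beta; 3, as in exclusion 1, is the natural choice. Make 4.5 match in region and start date.

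Three details matter:

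- Keeping the physical-dose limit avoids newly admitting conventional courses such as 40 Gy in 20.
- Restricting the equivalence limit to lung avoids barring patients whom neither text excludes now, for example after 20 Gy in 1 to a thoracic vertebra or rib that is not to be treated again.
- Counting from screening keeps the look-back of 4.5. Any radiotherapy between screening and randomisation is already barred by exclusion 15.

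The cost is one line in an amendment and a matching eligibility check. A few patients with recent lung SABR, number unknown, become ineligible in a 32-patient trial, and the physical-dose look-back lengthens by up to 28 days.

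If a plain limit of more than 36 Gy was intended, correct 4.5 instead and state why fraction size is ignored for pneumonitis risk.

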7.3 Patient Registration/Randomisation

Recruitment will cover a 2-year period. Screening for individual patients will take place within 28 days prior to randomisation onto the study.

The Investigator should ensure that all requirements are met prior to randomisation of eligible patients on the trial:

- Patient meets all inclusion and exclusion criteria requirements
- Patient has signed and dated all applicable consent forms
- All screening assessments have been completed and recorded in the patient's medical records complete with all relevant source documents

Eligible patients will be randomised electronically using the online SABRseq electronic data capture (EDC) system. Confirmation of randomisation and randomisation ARM will be provided electronically (via email) as well as, a unique 5-digit patient identification number.

Patients will not be randomised if treatment has commenced or if consent has not been given. Once a patient is randomised on a trial, randomisation will not be cancelled.

Following randomisation, patients should begin protocol treatment within 28 days

7.4 Treatment Assignment

Thirty-two patients will be randomised between the two arms in a 1:1 allocation ratio. Stratified randomisation will be used to assign the patients to the treatment arms. Stratification will occur by the number of metastases to be treated with SABR (two groups: 1 metastasis vs 2 or 3 metastases) and by line of therapy (two groups: previously untreated vs previously treated).

The next treatment to be assigned will not be known by any person prior to eligibility criteria being established and the intention to randomise the patient being declared.

7.5 Blinding and Procedures for Unblinding

This is an open-label trial; therefore, the Sponsor, investigator and patient will know the treatment administered

7.6 Patient Treatment Withdrawal/Discontinuation

Patients may withdraw consent at any time for any reason or be withdrawn from the trial treatment at the discretion of the investigator should any untoward effect occur. In addition, a patient may be withdrawn by the investigator or the Sponsor if continued enrolment into the trial is inappropriate for administrative and/or other safety reasons.

A trial patient may discontinue trial treatment for any of the following reasons:

- Disease progression
- Unacceptable adverse event
- Intercurrent illness which prevents further treatment
- Withdrawal of consent for treatment or from trial by the patient
- The investigator believes it is in the best interest of the patient
- The patient becomes pregnant or begins breastfeeding
- Noncompliance with the protocol

When a patient discontinues/withdraws prior to completion of protocol treatment, patients should attend the site for a 30-day (post end of trial treatment) safety follow-up visit for assessment of AEs and efficacy. Any AEs which are present at the time of

discontinuation/withdrawal should be followed in accordance with the safety requirements. The reason for discontinuation will be recorded on a CRF.

Discontinuation of trial treatment does not necessarily indicate withdrawal from the trial. Patients are expected to have follow-up assessments after treatment discontinuation if patients' agree and reason for trial treatment discontinuation permits.

Total withdrawal would occur in the circumstance that the patient decides to completely withdraw from all treatment aspects of the trial, and does not agree to any further scheduled follow up assessments. The patients' total withdrawal must be documented in the medical records and transcribed onto the relevant CRF. No further information will be collected from this patient for the purpose of this trial.

8. Study Assessments

The following assessments will occur during the trial. A schedule of assessments is provided on page 11.

